Post Market Clinical Follow-Up of the Zimmer Stafit Acetabular System

A multicenter, prospective, non-controlled study

PROTOCOL NO. 09-H07

NCT NUMBER: NCT04079114

PROTOCOL VERSION:
2011-11-14 - REV. 2

STUDY SPONSOR

ZIMMER GMBH
[name]
P.O. BOX
[name]
SWITZERLAND

Title:	Post Market Clinical Follow-Up Study of the Zimmer Stafit Acetabular System. A multicenter, prospective, non-controlled study.
Sponsor:	Zimmer GmbH
Objectives/ Endpoints:	
The objective of this study is to obtain outcome data on the Zimmer Stafit Acetabular System when used in primary total hip arthroplasty. This will be done by analysis of standard scoring systems, radiographs and adverse event records. Data will be used to monitor pain, mobility and implant survival, and to confirm the safety and performance of the Zimmer Stafit Acetabular System.
 
Primary endpoints:
 
• implant survival (Kaplan Meier)• dislocation rate at 2 years 
Secondary endpoints:
 
• pain and functional performance (HHS)• safety (adverse events)• radiographic parameters
Indication/Target Population:	Patients, suffering from severe hip pain and disability, requiring primary total hip arthroplasty with high risk of dislocation, who meet the inclusion/exclusion criteria (see Section Error! Reference source not found.).
Study Design:	Multi-center, prospective, non-controlled.
Clinical Phase:	Post-market
Number of subjects:	A total of 250 patients will be enrolled into the study.
Length of Study:	11.5 years (18 months enrollment plus 10 years follow-up): follow-up visits at 6-12 weeks, 1, 2, 3, 5, 7 and 10 years post-operatively.
Study Device:	Stafit Acetabular System
Scores:	Harris Hip Score (HHS)
Safety assessments:	Safety will be assessed by appropriate recording and reporting of adverse events throughout the study. All system components are CE marked and commercially available.
Statistical analysis:	Data collected will be summarized and reported to each participating Investigator. Statistical analysis is conducted by Zimmer or its designee.
Documentation:	Paper

General Statistical Method:

Data collected in the study will be summarized descriptively. Descriptive summaries will be used for the basis of all study reports, including a summary of the clinical performance of the Stafit Acetabular System in primary total hip arthroplasty, and may be used for reports and to support presentations and publications as needed.

Summaries will routinely describe categorical data as counts and percentages, and ninety-five percent confidence limits will be generally used to assess differences over time. Routine summaries describing continuous data will be in the form of means, medians, standard deviations, minima, and maxima, and ninety five percent confidence intervals will be used to contrast differences.

Routine summaries of implant survival will be described using the Kaplan-Meier method. Routine summaries of complication data will be in the form of frequencies and percentages. Summaries may be further generated for strata within the study population, such as males/females, body mass index or primary diagnosis.

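### Does using the data to confirm safety and performance require a benchmark and a survival time point in the plan?

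*Combined protocol and SAP*

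**What the plan says.** The synopsis, under Objectives/Endpoints, opens with the aim: "The objective of this study is to obtain outcome data on the Zimmer Stafit Acetabular System" in primary hip replacement. A later sentence on how the data will be used lists monitoring of pain, mobility and implant survival, and then adds "to confirm the safety and performance of the Zimmer Stafit Acetabular System". There are two primary endpoints: implant survival by Kaplan-Meier, with no time attached, and dislocation, which is fixed at 2 years. The design is multicentre, prospective and non-controlled.

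On size, the synopsis says "A total of 250 patients will be enrolled into the study" and gives no derivation. On timing, it lists "follow-up visits at 6-12 weeks, 1, 2, 3, 5, 7 and 10 years post-operatively".

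The General Statistical Method section states: "Data collected in the study will be summarized descriptively". It makes those summaries the basis of all study reports. For categorical data it adds that "ninety-five percent confidence limits will be generally used to assess differences over time". For the two primary endpoints the relevant sentences are "Routine summaries of implant survival will be described using the Kaplan-Meier method" and "Routine summaries of complication data will be in the form of frequencies and percentages". No hypothesis, reference rate, margin or acceptance limit appears in either section.

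**The concern.** To confirm something normally means that a result was possible which would not have confirmed it. Here no such result is written down. The 95% limits are meant for change over time, not for comparison with a standard, and complications are described by counts and percentages. Dislocation has a time point. Survival does not, and could be read at any of six annual visits (1, 2, 3, 5, 7 or 10 years).

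A sponsor that analyses its own data, or appoints the analyst, could thus settle on a benchmark and a favourable survival time point after seeing the results. It could then report that performance was confirmed. A reader could not tell which outcome would have led to the opposite statement. What is at stake is the strength of the claim in later reports and publications, not the validity of the estimates.

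**Working it through.** **The plan's own figure.** The 250 cannot be reproduced. The documents give no error rate, power, expected rate, margin, target precision or dropout, so no sample-size formula can be applied. What can be checked is what 250 patients deliver. Only the 250, the 2-year and 10-year times and the 95% level come from the documents. Every rate, hazard, benchmark and loss below is an assumption.

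**1. Precision for 2-year dislocation.** Exact (Clopper-Pearson) limits for x events in n patients are the 2.5% quantile of Beta(x, n−x+1) and the 97.5% quantile of Beta(x+1, n−x).

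| Events / n | Rate | 95% interval |
|---|---|---|
| 5/250 | 2.0% | 0.7 to 4.6% |
| 10/250 | 4.0% | 1.9 to 7.2% |
| 13/250 | 5.2% | 2.8 to 8.7% |
| 4/212 (15% lost) | 1.9% | 0.5 to 4.8% |
| 11/212 (15% lost) | 5.2% | 2.6 to 9.1% |

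These intervals follow from the counts that the plan already promises.

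**2. Precision for survival.** Take true 10-year survival S = 0.95 with complete follow-up. The Greenwood standard error is √(0.95 × 0.05 / 250) = 0.0138. On the log(−log) scale this is 0.0138 / (0.95 × 0.0513) = 0.283. The limits are 0.95 raised to the power exp(±1.96 × 0.283), that is 91.5% and 97.1%. With half the cohort censored by 10 years (exponential event and censoring times) they become 90.5% and 97.4%.

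**3. What the missing time point changes.** With a constant revision hazard h, S(t) = exp(−ht).

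| h per year | 2 years | 5 years | 10 years |
|---|---|---|---|
| 0.3% | 99.4% | 98.5% | 97.0% |
| 0.5% | 99.0% | 97.5% | 95.1% |
| 1.0% | 98.0% | 95.1% | 90.5% |

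The headline figure does depend on the year chosen. However, all entries in a row are points on one curve, and the curve is the planned output. Showing it reveals every time point at once.

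**4. What a formal rule would do.** Suppose confirmation required the upper 95% limit for dislocation to lie below a benchmark p₀. Let c be the largest event count that meets this. The chance of passing is then P(X ≤ c) with X binomial(n, p).

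| p₀ (assumed) | c at n = 250 | Pass if true rate is p₀ | Pass if true rate is p₀/2 |
|---|---|---|---|
| 5% | 5 | 1.3% | 40% |
| 8% | 11 | 1.8% | 70% |
| 10% | 15 | 1.8% | 81% |

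With 212 evaluable patients the counts are 4, 9 and 12, and the last column becomes 39%, 66% and 74%. For survival alone, take a 90% benchmark and a true 95% at 10 years. Simulation with log-log limits gives a pass chance of about 81%, 72% or 61% with 0%, 30% or 50% censored.

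A rule needing both endpoints is harder to meet. At the 5% dislocation benchmark with full follow-up, independence gives 0.404 × 0.813 = 0.33. Whatever the dependence, the joint chance lies between 0.404 + 0.813 − 1 = 0.22 and 0.40.

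**5. Side-by-side reading.** The aim is to obtain data, the design has no control, and the analysis is descriptive: these three agree. The verb *confirm* stands alone, in a sentence on use of the data, with no test or success claim attached to it anywhere. The sentence on complications does not rule out intervals. Dislocation is categorical, and the same section foresees 95% limits for categorical data, although their stated purpose is change over time.

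**The case for a change.** The strongest case for a change is that it would be cheap. Replacing the verb, naming one survival time point and promising an interval for each primary endpoint would need no extra patients. The plan shows, through dislocation, that it knows how to fix a time point. The summaries may support publications and the sponsor or its designee does the analysis, so advance specification would protect an outside reader against a standard chosen later. As the text stands, 5/250 and 13/250 could both be called confirmation.

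Most of this is factually right. There is no criterion, the time point is absent, and a report that claimed more than an estimate with its precision would go beyond what the plan supports.

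What does not follow is a need to alter the plan. The cheap version changes no estimate and no analysis: a competent analyst will show the curve with its limits and put an interval on the 2-year rate anyway. The stronger version requires benchmarks that the documents do not contain. Whether 250 patients suffice then depends wholly on the value assumed, with a pass chance at half the benchmark rate of 40% at 5% but 81% at 10%. Nothing in the documents suggests that a time point or standard will be picked after the fact.

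**Conclusion.** The observation is accurate, but it is a gap in detail and no change follows. The missing criterion sits behind one verb in a sentence on data use. The stated objective, the uncontrolled design and the descriptive analysis fit together, and carrying them out gives sound estimates of both primary endpoints: about 0.7 to 4.6% around an observed 2.0% dislocation rate, and about 91.5 to 97.1% around an assumed 95% survival at 10 years, both with complete data. The gap limits how strongly a report may speak and introduces no bias.

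Adding a pass/fail rule would turn a descriptive cohort into a different kind of study. Its pass chance could be as low as 40% for dislocation alone, and about 33% jointly with survival if the two are independent, under a 5% dislocation benchmark with a true rate of 2.5% and a 90% survival benchmark with a true 95% and full follow-up. All of those values are assumptions.

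The conclusion rests on reading the stated objective as governing the later sentence, and on the text at hand, which is a synopsis and a general statistical section. It would be different if the plan tied a formal success claim to either endpoint, which it does not.

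### Does describing 10-year implant survival by Kaplan-Meier alone, with no stated rule for deaths and no interval, call for a change to the plan?

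*Combined protocol and SAP*

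**What the plan says.** The synopsis lists "implant survival (Kaplan Meier") as the first of two primary endpoints. The stated length of study is "11.5 years (18 months enrollment plus 10 years follow-up"), and the sample size is given as "A total of 250 patients will be enrolled into the study".

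The General Statistical Method section says the study is summarised descriptively. Its only text on this endpoint is "Routine summaries of implant survival will be described using the Kaplan-Meier method".

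In the same section, the paragraph on categorical and continuous summaries provides for 95% limits. For categorical data it says "ninety-five percent confidence limits will be generally used to assess differences over time", and it makes a similar statement for continuous data. Complications are to be tabulated as numbers and proportions. The summaries "may be used for reports and to support presentations and publications as needed".

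Neither the synopsis nor the statistical section defines the failure event, states a censoring rule, attaches an interval to the survival curve, or mentions cumulative incidence with death as a competing event.

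**The concern.** Ten years is long enough for a noticeable share of hip arthroplasty patients to die with the implant still in place. A patient who has died can no longer be revised. If deaths are censored, one minus the Kaplan-Meier estimate is the revision risk in a hypothetical population in which nobody dies. As the share of enrolled patients who are actually revised it is too high, always in that direction, and more so as mortality rises. Because the summaries may reach publications, a reader could take the figure for a personal risk.

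Two omissions add to this. First, without a stated rule for deaths, the primary estimate is not fully determined by the plan. Second, the 95% limits are attached to categorical and continuous data and not to the survival curve, so a literal reading would allow a bare point estimate for a primary endpoint.

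**Working it through.** The plan has no figure to reproduce: 250 patients are stated without an event rate, precision target or loss assumption. The check is therefore an illustration under assumed rates.

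**Inputs.** From the documents: n = 250 and 10 years of follow-up. Assumed: failure means revision; net revision R = 5% at 10 years (3% and 10% as sensitivity); mortality M = 10% to 50% at 10 years; independent hazards; deaths are the only censoring before year 10.

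**Formulas, constant hazards.**
- Revision hazard: r = -ln(1 - R)/10 = -ln(0.95)/10 = 0.00513 per year.
- Death hazard: m = -ln(1 - M)/10, which is 0.01054 at M = 10% and 0.06931 at M = 50%.
- Net risk, the target of one minus Kaplan-Meier: 1 - exp(-10r) = 5%.
- Cumulative incidence with death competing: r/(r + m) × (1 - exp(-10(r + m))).
- Greenwood variance of log survival: (r/n) × (exp(10(r + m)) - 1)/(r + m). The half-width is 1.96 × 0.95 × the square root of this.

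Worked case, M = 50%: r + m = 0.07444 and exp(-0.7444) = 0.95 × 0.50 = 0.475. Cumulative incidence = (0.00513/0.07444) × 0.525 = 3.62%, so the gap is 5.00 - 3.62 = 1.38 points. Variance = (0.00513/250) × (1/0.475 - 1)/0.07444 = 0.000305; half-width = 1.96 × 0.95 × 0.01745 = 3.25 points.

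The front-loaded variant puts half of the cumulative revision hazard in year 1 and spreads the rest evenly over years 2 to 10.

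| 10-year mortality | Cumulative incidence, constant | Gap (points) | Cumulative incidence, front-loaded | Gap (points) | 95% half-width, constant (points) |
|---|---|---|---|---|---|
| 10% | 4.75% | 0.25 | 4.85% | 0.15 | 2.78 |
| 20% | 4.49% | 0.51 | 4.69% | 0.31 | 2.86 |
| 30% | 4.21% | 0.79 | 4.53% | 0.47 | 2.96 |
| 40% | 3.92% | 1.08 | 4.35% | 0.65 | 3.09 |
| 50% | 3.62% | 1.38 | 4.16% | 0.84 | 3.25 |

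Front-loaded half-widths are 2.7 to 3.0 points. A simulation with 250 patients and 3,000 runs under constant hazards gave means of 5.0% (Kaplan-Meier) against 4.2% (Aalen-Johansen) at 30% mortality, and 5.1% against 3.7% at 50%.

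**Sensitivity, constant hazards.** At 3% net revision the gap is 0.15 to 0.83 points against half-widths of 2.17 to 2.54. At 10% it is 0.50 to 2.74 points against 3.82 to 4.48. The gap stays below the half-width throughout.

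**Earlier times, 5% net revision at 10 years.** At 5 years the gap is about 0.07 to 0.39 points (constant) or 0.05 to 0.29 (front-loaded), against half-widths of about 2.0 to 2.4. At 2 years the ratio of net to actual risk is at most 1.07.

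**Interval.** The expected log-log 95% interval around 95% survival at 10 years is 91.3% to 97.1% at 10% mortality (about 214 at risk) and 90.5% to 97.4% at 50% (about 119 at risk). Loss to follow-up would widen it.

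**Counting deaths as failures.** The estimated failure would be 1 - 0.95 × (1 - M), that is 14.5% at 10% mortality and 52.5% at 50%. That measures patients alive with the implant in place, not survival of the implant, so the endpoint's name already points to censoring.

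**The case for a change.** The strongest argument for acting is that in a descriptive study the estimate is the result, so the plan should say what is being estimated and how precisely. The spread from 5% to 52.5%, depending on how deaths are treated, shows that the rule is not trivial. The interval spans about 6 to 7 points, which a bare point estimate would hide. The gap between net and actual risk is systematic, so being smaller than sampling error does not remove it. Stating the conventions would take two or three sentences.

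Much of this stands. The omissions are real, and the failure event is the most basic of them. The complication tables do not fully close the gap either: they might yield a crude proportion revised, but revision is not named there and a crude proportion does not handle incomplete follow-up.

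What does not stand is that the analysis as written would go wrong. Censoring deaths is the usual convention for implant survival. A Kaplan-Meier summary ordinarily comes with Greenwood limits, and the plan already uses 95% limits for its other summaries. The Aalen-Johansen estimate is a sound addition for anyone wanting a patient's own revision risk, but that is a different question from the device's performance, and the plan does not pose it.

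**Conclusion.** No change is called for. The text omits detail that an analyst would fill sensibly, and Kaplan-Meier suits the stated aim. With revision as failure and deaths censored, it estimates net implant survival validly.

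If its complement were misread as patients' actual revision risk, the overstatement at 10 years would be 0.15 to 1.4 points across the two hazard shapes at 5% net revision. The top of that range needs 50% mortality. Sampling error at n = 250 is 2.7 to 3.3 points either way. The study has no hypothesis or success threshold in the text, so no stated decision moves.

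The sizes rest on assumed revision and mortality rates and independent hazards, since the documents give no age, mortality or revision figures. The conclusion is limited to the published synopsis and general statistical section. If a later report makes statements about patients' own chance of revision, a 10-year cumulative incidence with death as a competing event would be the right figure for them; it can be added at reporting, provided dates of revision and death are recorded, which the text does not say.

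### The primary 2-year dislocation rate would by default be a crude percentage with no stated denominator; a cumulative incidence that censors lost patients is a cheap improvement

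*Combined protocol and SAP*

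**What the plan says.** The synopsis row on objectives and endpoints lists two primary endpoints. Implant survival has its method, Kaplan-Meier, beside it in brackets. The other is given only as "dislocation rate at 2 years", without definition, estimator or denominator. The synopsis plans 250 patients and "follow-up visits at 6-12 weeks, 1, 2, 3, 5, 7 and 10 years post-operatively".

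The General Statistical Method section opens with "Data collected in the study will be summarized descriptively". On time-to-event methods it says "Routine summaries of implant survival will be described using the Kaplan-Meier method". It never mentions dislocation. Two generic rules come nearest: "Summaries will routinely describe categorical data as counts and percentages" and "Routine summaries of complication data will be in the form of frequencies and percentages".

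Neither part states whose dislocations count, over which patients, or how a patient who dies, has the cup removed or is lost before 2 years enters the calculation.

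**The concern.** Dislocation is both a complication and a yes/no outcome, so the generic rules lead to a plain percentage. A plain percentage at 2 years treats a patient seen for 3 months and one seen for 24 months alike, or drops one of them, depending on the denominator. The other primary endpoint is protected from this by Kaplan-Meier; this one is not.

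Four percentages would all be consistent with the text:

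- (a) recorded dislocators over all enrolled: slightly too low, because dislocations after loss are unseen;
- (b) all recorded dislocators over patients who reach 2 years: too high;
- (c) all recorded dislocators over dislocators plus event-free completers: too high;
- (d) dislocators among patients who reach 2 years, over those same patients: close to unbiased if loss is unrelated to dislocation, but it discards recorded events and falls too low if patients leave more often after dislocating.

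In an uncontrolled descriptive study the reported rate is itself the result. Its confidence interval shows sampling error but not the effect of the denominator. If the choice is left open until the data are seen, a primary figure has avoidable flexibility.

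**Working it through.** **What can be reproduced.** The plan gives no expected dislocation rate, precision target or loss rate, so it has no figure of its own to recompute. The only input from the documents is N = 250 (synopsis). Everything else below is assumed for illustration.

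**Base-case assumptions.** Net 2-year dislocation risk 5%, of which 60% (3 percentage points) falls in the first 3 months; 8% death and 10% loss over 24 months; all three independent, with hazards constant within each period.

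**Monthly hazards.**
- Dislocation, months 0-3: -ln(0.97)/3 = 0.01015
- Dislocation, months 3-24: -[ln(0.95) - ln(0.97)]/21 = 0.00099
- Death: m = -ln(0.92)/24 = 0.00347
- Loss: c = -ln(0.90)/24 = 0.00439

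**Target and recorded events.** Let h(t) be the dislocation hazard and S(t) the net dislocation-free probability.
- True cumulative incidence = integral over 0-24 of h(t) S(t) exp(-m t) dt = 4.89%
- Recorded incidence = integral over 0-24 of h(t) S(t) exp(-(m + c) t) dt = 4.766%, or 250 x 0.04766 = 11.92 dislocators
- Reaching 2 years: 250 x 0.92 x 0.90 = 207, of whom 207 x 0.05 = 10.35 dislocated and 196.65 did not

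**The four percentages.**
- (a) 11.92/250 = 4.77%
- (b) 11.92/207 = 5.76%
- (c) 11.92/(11.92 + 196.65) = 5.71%
- (d) 10.35/207 = 5.00%

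**Other assumed rates, same formulas.**

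| Net risk / death / loss | True | (a) | (b) | (c) | (d) |
|---|---|---|---|---|---|
| 5% / 8% / 10% | 4.89% | 4.77% | 5.76% | 5.71% | 5.00% |
| 5% / 8% / 5% | 4.89% | 4.83% | 5.53% | 5.50% | 5.00% |
| 5% / 10% / 15% | 4.87% | 4.68% | 6.11% | 6.04% | 5.00% |
| 10% / 8% / 10% | 9.79% | 9.53% | 11.51% | 11.34% | 10.00% |

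**Against sampling error.** The standard error is about sqrt(0.0489 x 0.9511/250) = 1.4 points. In the base case (a) is off by about 0.1 point (0.1 SE), (d) by about 0.1 point, (c) by 0.8 and (b) by 0.9 (0.6 SE). Exact 95% limits for 12/250 are 2.5% to 8.2%.

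**Loss that rises after a dislocation.** Multiplying the loss hazard by 3 or 5 after the first dislocation lowers (d) to 4.32% or 3.74%. Reading (a) stays at 4.77%, and an estimator that counts the first dislocation when it happens stays at 4.89%. At 5 times, (b) is 5.83%, so (b) and (d) are 5.83 - 3.74 = 2.1 points apart on the same data.

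**A check without the hazard model.** Take 10 recorded dislocations and 50 of 250 patients lost event-free. All enrolled gives 10/250 = 4.00%; the actuarial form gives 10/(250 - 25) = 4.44%; leaving out the lost gives 10/200 = 5.00%. With no loss the three agree.

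**The case against.** Four arguments weigh against the point.

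1. A reader might infer that the plan gives this endpoint no estimator at all. The text does not support that: the rules for categorical and complication data cover dislocation on an ordinary reading and imply a crude percentage. What is absent is the denominator and any allowance for incomplete follow-up.
2. A reader might also infer that the sponsor has no such rule anywhere. That cannot be known. The public text is a synopsis and one short methods section, and the synopsis refers to a section on eligibility that is not visible. A fuller protocol may define the endpoint, in which case a reference to it would answer the missing-denominator part.
3. The effect is small for the natural readings. All-enrolled and completers-only differ by 5.00 - 4.77 = 0.23 points in the base case. The upper end of the spread needs a mixed denominator. Reading (b) counts some patients above the line who are missing below it, which is closer to an error than an interpretation. Reading (c) does not have that flaw, however, and still lies 0.94 points above (a).
4. One sentence naming numerator, denominator and number lost would remove the ambiguity without a new method.

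The first three stand and limit the claim. The fourth stands in part: the sentence would fix the wording, but the percentage would still ignore unequal follow-up. The time-to-event alternative uses every recorded dislocation and belongs to the same family of methods already planned for the other primary endpoint.

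**Conclusion.** The point holds as a cheap improvement of minor severity. By default the dislocation endpoint is a crude percentage without a stated denominator. Under the base-case assumptions the readings run from 4.77% to 5.76% around a true 4.89%, a spread of about 1 point, which is less than the standard error of about 1.4. Completers-only can fall to 3.74%, but only if loss is 5 times higher after a dislocation.

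It would be tempting to conclude that the trial's primary result is unreliable or that a conclusion is at risk. The documents do not support that: the analysis is descriptive, no hypothesis or threshold is stated, and every dislocation, death and loss rate used here is assumed. Cup removal was not modelled, so its effect is not quantified.

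**What to change.** Define the primary estimate as the 24-month cumulative incidence of first dislocation of the study hip, counted once per patient, with a 95% CI. Censor lost patients at last contact and treat death and removal of the study cup as competing events (Aalen-Johansen). One minus Kaplan-Meier is acceptable if labelled as net risk. Beside it, report the crude count with its numerator and denominator and the number lost before 24 months, and state the assumption that loss before dislocation is non-informative.

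**Cost.** One paragraph of analysis text and one extra analysis. Dates of first dislocation, death, cup removal and last contact are needed. The synopsis says of the data sources "This will be done by analysis of standard scoring systems, radiographs and adverse event records", which does not show whether all these dates are collected.

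**Precision.** In 10,000 simulated base-case trials of 250, the mean 95% CI width was 5.62 points for Aalen-Johansen, 5.65 for all enrolled (exact) and 6.38 for completers only (exact). With 10% death and 15% loss the widths were 5.66, 5.61 and 6.66. Exact widths depend somewhat on the interval method, but there is no material loss against all enrolled.

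**What it does not cure.** Loss related to dislocation risk before the event still biases the estimate. If 20% of patients have 3 or 5 times both hazards, with overall rates kept, the true value is 4.89%. Aalen-Johansen then gives 4.85% or 4.79%, all enrolled 4.73% or 4.67%, and completers only 4.84% or 4.61%. The bias is smaller, not removed.

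### Crude complication percentages over up to 10 years would modestly understate long-term risk if patients are lost; adding cumulative incidence for key complications is a cheap improvement

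*Combined protocol and SAP*

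**What the plan says.** The relevant text is in the synopsis and the General Statistical Method section of the combined protocol and SAP.

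- **Complications.** "Routine summaries of complication data will be in the form of frequencies and percentages". For categorical data in general, the same section adds 95% confidence limits.
- **Implant survival.** The sentence just before reads: "Routine summaries of implant survival will be described using the Kaplan-Meier method".
- **Recording period.** The Safety assessments row of the synopsis says: "Safety will be assessed by appropriate recording and reporting of adverse events throughout the study". The Length of Study row gives 10 years of follow-up per patient, with visits at 6-12 weeks and at 1, 2, 3, 5, 7 and 10 years.
- **Endpoints.** Adverse events are a secondary endpoint without a time point. One complication has its own time point as a primary endpoint: "dislocation rate at 2 years".
- **Use.** The Objectives row says that the data serve "to confirm the safety and performance of the Zimmer Stafit Acetabular System". The method section says: "Descriptive summaries will be used for the basis of all study reports".

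Neither place says how loss to follow-up, withdrawal or death is handled when a complication percentage is formed.

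**The concern.** Two outcomes followed over the same years in the same patients are handled differently. Kaplan-Meier allows for patients whose follow-up ends early; a crude percentage does not. A patient lost at year 3 with no complication stays in an all-enrolled denominator as if known to be free of complications to year 10, so any later event is missed and the percentage falls below the 10-year risk.

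This matters somewhat more because the study has no control group. The absolute percentage is the safety result, and a downward bias cannot cancel in a comparison between groups. Revision could then be reported with allowance for incomplete follow-up, and other complications without it, side by side in one report.

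**Working it through.** **Figures in the documents.** There is no complication risk, loss rate or precision target to reproduce. Enrolment is 250 patients. The study length is consistent: 1.5 + 10 = 11.5 years.

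**Assumptions.** True 10-year risk F is 10% or 20%. Cumulative 10-year loss L is 10, 20, 30 or 40%. Loss is independent of events, hazards are constant, and there are no deaths at first. Percentages are of patients with at least one event, divided by all enrolled.

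**Formula.** Event hazard a = -ln(1-F)/10 and loss hazard c = -ln(1-L)/10. The expected all-enrolled percentage is

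E = a/(a+c) × [1 - (1-F)(1-L)].

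**Example, F = 10%, L = 30%.** a = 0.01054 and c = 0.03567, so a/(a+c) = 0.228. The bracket is 1 - 0.9 × 0.7 = 0.37. E = 0.228 × 0.37 = 8.4%, or about 21 of 250 patients with an observed event, against 25 with complete follow-up.

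| Assumed loss | F = 10%: shown (shortfall, points) | F = 20%: shown (shortfall, points) |
|---|---|---|
| 10% | 9.5% (0.5) | 19.0% (1.0) |
| 20% | 9.0% (1.0) | 18.0% (2.0) |
| 30% | 8.4% (1.6) | 16.9% (3.1) |
| 40% | 7.9% (2.1) | 15.8% (4.2) |

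**Sampling error for scale.** The half-width is 1.96 × sqrt(F(1-F)/250): 3.7 points at 10% and 5.0 at 20%. The shortfall is smaller in every row.

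**Early events.** Let 8 of the 10 points fall in year 1, so the hazard is -ln(0.92) = 0.0834 in year 1 and ln(0.92/0.90)/9 = 0.00244 a year after that. With 30% loss, year 1 contributes 7.9% and later years 1.7%. The unrounded total is 9.5%, a shortfall of 0.5 points.

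**Deaths.** Take F = 20% (the risk in the absence of death) and 30% deaths, with death hazard d = -ln(0.7)/10.
- True cumulative incidence with death competing: a/(a+d) × (1 - 0.8 × 0.7) = 0.385 × 0.44 = 16.9%.
- With no loss, the all-enrolled percentage equals this exactly.
- With 30% loss as well: a/(a+c+d) × (1 - 0.8 × 0.7 × 0.7) = 0.238 × 0.608 = 14.5%.

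**The alternative estimator.** With independent loss, Aalen-Johansen targets the true figure; at F = 10% and L = 30%, simulation gave a mean of 10.0%. Its standard deviation was 2.1 points, against 1.8 for the crude percentage. With informative loss (half the patients having three times the event hazard and three times the loss hazard; overall risk 10%, loss 30%), the crude figure is 8.1% and Aalen-Johansen 9.6%. It removes most of the bias in that example, but not all.

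**The case against.** The strongest reply is that the plan is descriptive and does what it says. Adverse events are a secondary endpoint with no target risk, and crude counts are a legitimate account of what was recorded. That stands. A reader might infer that the plan presents these percentages as 10-year risks, or that they are unusable. The documents support neither: confirming safety is a general objective, not a stated 10-year estimand, and the percentages mislead only if read as long-term risk.

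A reader might also infer that crude percentages are the sole summary. The text describes routine summaries, which does not exclude others, and confidence limits apply generally. Neither allows for loss, however.

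A larger effect can be obtained by dividing instead by patients with an event plus those followed event-free to 10 years. At 30% loss, 10% then becomes 8.4/(8.4 + 63.0) = 11.8%, and the gap between the two denominators is 3.4 points (6.3 at 20% risk). No section mentions such a denominator. The only patient count given is the 250 enrolled, so these gaps should not be attributed to the plan.

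The contrast with Kaplan-Meier is not a contradiction. Complications are of many types and can recur, so a different summary is a defensible choice. Dislocation already has a 2-year time point, and complications that end in implant failure may enter the survival analysis. The available document is also short, and a fuller plan may say more.

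What remains is that, for other key complications, the stated routine summary makes no allowance for incomplete follow-up, and a better method is available at little cost.

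**Conclusion.** The point holds as a low-severity improvement. With all enrolled patients as the denominator and independent loss of 10 to 40%, the crude percentage understates 10-year risk by 0.5 to 2.1 points when that risk is 10%, and by 1.0 to 4.2 points when it is 20%. This is systematic but within sampling error at 250 patients. It is smaller with early events and absent when death alone shortens follow-up. The sizes rest on assumed risk, assumed loss, constant hazards and patient-level percentages. The direction needs only some loss of patients still at risk of a first event.

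**What to change.** Keep the crude counts and percentages, per enrolled patient, with the numbers lost, withdrawn and dead beside them. Add to the General Statistical Method section that, for key device- or procedure-related complications prespecified by the sponsor, the cumulative incidence of first event will be reported at scheduled visit times, for example 2, 5 and 10 years. Estimate it by Aalen-Johansen, with death as a competing event and loss or withdrawal censored, and give 95% confidence intervals and numbers at risk.

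The cost is a paragraph of SAP wording, a few more tables, and a check that complication onset dates are recorded. Last-contact dates are already needed for Kaplan-Meier. No extra patients or visits are required. The figures will be slightly more variable and may look slightly less favourable than the crude percentages. Informative loss is not corrected, and reports should say so. If a fuller version of the plan already contains such an analysis, a cross-reference is enough.
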